5.2. Participant and Study Completion

A maximum of 24 participants, 12 participants with evidence of BAM and 12 participants without evidence of BAM will receive study treatment such that approximately 24 evaluable participants complete the study.

5.3. End of Study Definition

The end of the study is defined as the date of Visit 6 (post-treatment follow-up visit).

A participant is considered to have completed the study if he/she has completed all periods of the study including post-treatment follow-up visit.

5.4. Scientific Rationale for Study Design

This is an open-label, cohort controlled study designed to evaluate the comparative effects of eluxadoline on the altered bowel function in IBS-D participants with and without evidence of BAM. This non-randomized design is considered most appropriate since the cohort assignment will be based on the determination of BAM status.

A primary factor in the design of this study is the mechanism by which evidence of BAM will be established and documented in the patient population. Both the Rome IV criteria and EMA guideline for IBS suggest that the results from a therapeutic study with a bile acid binding agent can be an appropriate surrogate given that these agents have been shown to improve stool passage and stool consistency in patients with BAM ([Wong 2012](#); [Bajor 2015](#)). While empiric studies of sequestrants such as cholestyramine or colestevolam have the advantage of being clinically applicable, they provide only indirect evidence of BAM since these agents can have nonspecific effects to ameliorate diarrhea of other causes ([Camilleri 2015](#)). Additionally, therapeutic studies of cholestyramine are hampered by tolerability and compliance issues owing to its poor palatability and potential side effects, while studies of the newer agent colestevolam are hampered by its expense ([Camilleri 2014](#)).

Most potentially direct diagnostic tests of BAM are limited in their availability and/or clinical practicality. The most definitive test is the measurement of fecal bile acids in a 48-hour stool collection. Measurement of fecal bile acids is a direct measure of excess bile acids entering the colon. Primary fecal bile acids [Chenodeoxycholic acid (CDCA) and cholic acid (CA)] are significantly higher in patients with BAM and correlate with stool frequency and consistency ([Shin 2013](#), [Wong 2012](#)). A potential alternative, the nuclear medicine SeHCAT test which measures bile acid retention is more clinically practical but does require 2 separate clinical visits to determine SeHCAT retention after a week. While SeHCAT testing has been the primary measure by which the overlap of BAM and IBS-D has been identified, it is not approved for use in the United States and is not widely available in the rest of the world ([Islam 2012](#)). Total fecal bile acids $\geq 2337 \mu\text{mol}/48 \text{ hr}$ is the gold standard for BAM diagnosis in countries where SeHCAT retention is not available ([Shin 2013](#)).

The typical proportion of primary fecal bile acids in healthy volunteers is $\sim 0.2\%$. Patients with BAM have higher stool weight compared to those with chronic diarrhea without BAM or healthy volunteers ([Vijayvargiya 2018](#)). The sensitivity and specificity of the fecal biomarkers of BAM are listed in [Table 5-2](#). Therefore, elevated primary BA alone or in combination with total fecal bile acids of $\geq 1000 \mu\text{mol}/48 \text{ hr}$ have a similar diagnostic accuracy as total fecal BA alone of $> 2337 \mu\text{mol}/48 \text{ hr}$ in detecting elevated fecal weight in patients with BAM. Statistical analysis has demonstrated no significant difference between the ROC curve to estimate elevated fecal weight for either total BA or elevated primary fecal BA ($p=0.13$). After increasing the primary

Eluxadoline

BA cutoff to 10% or higher with total fecal BA $\geq 1000 \mu\text{mol}/48 \text{ hr}$, there was no significant gain in either sensitivity (41%) or specificity (97%) compared to the lower cutoff of primary BA $\geq 4\%$ with total fecal BA $\geq 1,000 \mu\text{mol}/48 \text{ hr}$ ([Vijayvargiya 2018](#)).

Therefore, even at the lower cutoff values of $\geq 4\%$, primary fecal bile acids are indicative of BAD even though the total fecal BA may be only $1000 \mu\text{mol}/48 \text{ hr}$.

However, in an analysis of 986 patients who underwent 48 hour fecal BA evaluation for chronic diarrhea, 26% of patients had elevated total fecal bile acids whereas 46% of patients had fecal primary bile acids $\geq 10\%$, indicating that measuring total fecal bile acids alone will miss a subgroup of patients who have features of BAM ([Vijayvargiya 2018](#)).

Evidence has suggested that measurement of serum 7α -hydroxy-4-cholesten-3-one ($7\alpha\text{C}4$ test) may also be an effective indicator of BAM. Serum $7\alpha\text{C}4$ is a surrogate for hepatic BA synthesis rate and has been demonstrated to be elevated in patients with BAM ([Eusufzai 1993](#)) and in some patients with IBS-D ([Odunsi-Shiyanbade 2010](#); [Wong 2012](#)). The use of serum $7\alpha\text{C}4$ to diagnose BAM has been validated against SeHCAT testing and was demonstrated to have approximately 90% sensitivity and 79% specificity ([Sauter 1999](#)). The fasting (6-10 am) serum $7\alpha\text{C}4$ test is considered most ideal because of its simplicity, as collection of blood for $7\alpha\text{C}4$ analysis can occur as part of the routine screening process for the study. The analysis of serum $7\alpha\text{C}4$ levels requires a liquid chromatography-tandem mass spectrometry (LC-MS/MS) method which is currently available ([Camilleri 2009](#); [Camilleri 2014a](#)). Further, serum $7\alpha\text{C}4$ was demonstrated to have high positive and negative predictive values making it attractive as a diagnostic test of BAM. Therefore, in this study, BAM status will be determined by the presence of at least one of the parameters listed in [Table 5-2](#).

The sample size is based primarily on clinical considerations, including the desire to minimize the number of potential clinical sites given the possible need to utilize a research laboratory for analysis of screening serum $7\alpha\text{C}4$ samples. While not statistically powered, the study sample is considered sufficient to characterize the effects of eluxadoline on the altered bowel function of IBS-D patients with BAM and to qualitatively evaluate whether these patients respond differently to eluxadoline treatment.

The duration of treatment was chosen to be consistent with clinical practice in IBS, where a 1-month therapeutic study of a new agent is common and is supported by results of the Phase 3 studies which showed that a patient's response to eluxadoline treatment over the first month is reasonably predictive of responsiveness over longer durations. The post-treatment period is intended to allow for an off-treatment assessment of safety.

The study will enroll an IBS-D population similar to that enrolled in the Phase 3 studies of eluxadoline. Participants will meet the Rome IV criteria for IBS-D, which differs from the Rome III criteria used in the Phase 3 studies primarily in eliminating abdominal discomfort as a distinct entity from abdominal pain in the definition of IBS-D ([Lacy 2016](#)). Evidence of BAM will be determined by a screening serum $7\alpha\text{C}4$ value $\geq 52.5 \text{ ng/mL}$, which has previously been utilized as a diagnostic cutoff for BAM based on this value being greater than the 95th percentile of serum $7\alpha\text{C}4$ values from 184 healthy controls ([Vijayvargiya 2017](#)).

In order to have comparable treatment groups, the cohorts will be matched to the highest extent possible by age, gender and severity of historic symptoms based on the investigator's discretion.

Improvements in bowel symptoms will be measured during the study. Stool consistency is a highly sensitive efficacy marker, making it ideally suitable to detect potential differences in responsiveness to treatment among participants with and without evidence of BAM. The primary outcome measure for this study will therefore be changes from baseline in stool consistency scores over the 4-week treatment period. Changes from baseline are considered more appropriate than monthly responder definitions given the small pilot nature of this study.

Table 5-2 Current and future and bile acid diarrhea (BAD) diagnostic tests

Diagnostic Test	Fasting serum C4	Total fecal BA	Primary BA >4% + total fecal BA	Fecal primary BA >10%
What does it measure	Hepatic bile acid synthesis	Total fecal bile acid excreted from the colon	Amount of bile acids with secretory potential with total fecal BA excretion	Amount of bile acids that are directly synthesized from the liver with secretory potential
Diagnostic Cutoffs	$\geq 52.5 \text{ ng/mL}$	$\geq 2,337 \mu\text{mol}/48\text{h}$	Primary BA $\geq 4\%$ + total fecal BA $\geq 1,000 \mu\text{mol}/48\text{h}$	$\geq 10\%$ Primary BA
Sensitivity relative to fecal weight $>400\text{g}/48\text{h}$	15%	59%	46%	49%
Specificity relative to fecal weight $>400\text{g}/48\text{h}$	86%	92%	97%	91%

Source: [Vijayvargiya 2018](#)

5.5. Justification for Dose

The 100 mg BID dose selected for this study is consistent with US and global labeling for eluxadoline in IBS-D.

6. Study Population

Prospective approval of protocol deviations to recruitment and enrollment criteria, also known as protocol waivers or exemptions, is not permitted.

6.1. Inclusion Criteria

Participants are eligible to be included in the study only if all of the following criteria apply:

1.	Age/Sex
1.01	Participant is a man or woman aged 18 to 75 years, inclusive, at screening.
2.	Type of Participant and Disease Characteristics
2.02	Participant has a diagnosis of IBS with predominant diarrhea (IBS-D) defined by the Rome IV criteria as > ¼ (25%) of bowel movements with BSFS score of 6 or 7 and < ¼ (25%) of bowel movements with BSFS score of 1 or 2.
2.03	
Participants with evidence of BAM: Participants must have at least one of the following at screening or within 1 calendar year prior to screening.
 
 • fasting serum 7a-hydroxy-4-cholest-3-one (7αC4) level \geq 52.5 ng/mL • total fecal bile acids $>$ 2337 micromoles/48 hours • primary bile acids (fecal CA and CDCA) \geq 10% in a 48h fecal collection • primary bile acids (fecal CA and CDCA) \geq 4% with total fecal bile acid \geq 1,000 micromoles/48hr

2.04	
Participants without BAM: Participants must have at least one of the following at screening or within 1 calendar year prior to screening.
 
 • fasting serum 7αC4 level ≤ 47.1 ng/mL • fasting serum 7αC4 levels > 47.1 ng/mL but < 52.5 ng/mL with fecal bile acids that are negative for bile acid malabsorption (i.e. do not meet criteria 2.03 based on fecal bile acids level) • total fecal bile acids (BA) ≤ 2337 micromoles/48 hours • primary bile acids (fecal CA and CDCA) $< 10\%$ in a 48h fecal collection • primary bile acids (fecal CA and CDCA) $< 4\%$ with total fecal bile acid $< 1,000$ micromoles /48hr
2.05	
Participant meets the colonoscopy requirements defined in Appendix 10 Section 12.10, which are modified from the Summary of the US-Multi-Society Task Force on Colorectal Cancer and other Colonoscopy Requirements

2.06	
Participant has an average daily BSFS score ≥ 5.0 or at least 25% of days of diary entry with a BSFS score of 6 or 7 during the 14 days prior to Day 1 of study treatment

3.	
Contraceptives

3.01	
A sexually active woman of childbearing potential (WOCBP), as defined in Appendix 5, Section 12.5 must agree to follow the contraceptive guidance given in Appendix 5, Section 12.5 from the date she provides informed consent until 24 hours after her final dose of study drug.

4.	
Informed Consent

4.01	
Participant must sign an informed consent form (ICF) before the initiation of any study-related procedures indicating that he or she understands the purpose of and procedures required for the study and is willing to participate in the study.

5.	
Other

5.01	
Participant has completed the eDiary on at least 10 of the 14 days prior to Day 1 of study treatment.

5.02	
Participant has not used loperamide rescue medication on more than 3 days in the 14 days prior to Day 1 of study treatment (see Section 7.7.3).

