^a Screening and pretreatment periods may be combined, if results of fasting serum 7 α C4 test or 48-hour fecal BA collection conducted within 1 calendar year from screening are available at the time of the combined visit or results from fasting serum 7 α C4 test are available prior to the start of study treatment.

^b May be done over the phone.

The total duration of study participation for each participant will be up to 11 weeks.

Key inclusion criteria:

1. Adult men or women aged 18 to 75 years inclusive with a diagnosis of IBS-D per Rome IV criteria.
2. Participants with evidence of BAM must have at least one of the following at screening or within 1 calendar year prior to screening:
 - fasting serum 7 α -hydroxy-4-cholesten-3-one (7 α C4) level \geq 52.5 ng/mL
 - total fecal bile acids $>$ 2337 micromoles/48 hours
 - primary bile acids (fecal CA and CDCA) \geq 10% in a 48h fecal collection
 - primary bile acids (fecal CA and CDCA) \geq 4% with total fecal bile acid \geq 1,000 micromoles/48hr
3. Participants without BAM must have at least one of the following at screening or within 1 calendar year prior to screening:
 - fasting serum 7 α C4 level \leq 47.1 ng/mL
 - fasting serum 7 α C4 levels $>$ 47.1 ng/mL but $<$ 52.5 ng/mL with fecal bile acids that are negative for bile acid malabsorption (i.e. do not meet criteria 2.03 based on fecal bile acids level)
 - total fecal bile acids (BA) \leq 2337 micromoles/48 hours

Eluxadoline

- primary bile acids (fecal CA and CDCA) < 10% in a 48h fecal collection
- primary bile acids (fecal CA and CDCA) < 4% with total fecal bile acid < 1,000 micromoles /48hr

4. An average daily Bristol Stool Form Scale (BSFS) score ≥ 5.0 or $\geq 25\%$ of diary entry days with a BSFS score of 6 or 7 during the 14 days prior to Day 1.
5. Women of childbearing potential must use hormonal or double barrier contraception or maintain a monogamous relationship with a vasectomized male partner from the date of informed consent until 24 hours after final dose of study drug.
6. Completed the electronic diary (eDiary) on ≥ 10 of the 14 days prior to Day 1.
7. Has not used loperamide rescue medication on > 3 of the 14 days prior to Day 1.

Key exclusion criteria:

1. A diagnosis of IBS with a subtype of irritable bowel syndrome with constipation (IBS-C), mixed IBS, or unsubtyped IBS per Rome IV criteria.
2. Does not have a gallbladder.

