7.3. Method of Treatment Assignment

This is an open-label, parallel-group study. Eluxadoline 100 mg BID will be administered to all participants in the study after they are qualified based on meeting all eligibility criteria.

Participants will be stratified into 2 cohorts: IBS-D participants with evidence of BAM and IBS-D participants without evidence of BAM. As far as possible, the 2 cohorts will be matched by age, gender and severity of historic symptoms based on the investigator's discretion. Study participants who have discontinued the study may not be replaced.

[figure not shown]

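### The BAM and non-BAM entry lists overlap, so a participant who meets a BAM criterion can be placed in the comparator cohort

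*Protocol*

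**What the plan says.** Protocol Section 6.1 sets two parallel entry criteria. For criterion 2.03 the rule is "Participants with evidence of BAM: Participants must have at least one of the following at screening or within 1 calendar year prior to screening". Four items follow: serum 7αC4 of at least 52.5 ng/mL; total fecal bile acids above 2337 micromoles/48 h; primary bile acids of at least 10%; or primary bile acids of at least 4% with a total of at least 1,000.

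For criterion 2.04 the rule is "Participants without BAM: Participants must have at least one of the following at screening or within 1 calendar year prior to screening". Five items follow: serum of 47.1 or below; serum between 47.1 and 52.5 with fecal results that do not meet 2.03; total of 2337 or below; primary below 10%; or primary below 4% with total below 1,000. The Synopsis repeats both lists ("Participants without BAM must have at least one of the following at screening or within 1 calendar year prior to screening").

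Section 5.4 states how status is decided in two ways. One sentence says "BAM status will be determined by the presence of at least one of the parameters listed in" Table 5-2. A later one says "Evidence of BAM will be determined by a screening serum" 7αC4 value of 52.5 ng/mL or more, with no mention of fecal results.

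Section 7.3 says "Participants will be stratified into 2 cohorts: IBS-D participants with evidence of BAM and IBS-D participants without evidence of BAM". SAP Section 4.0 bases cohort on BAM status, and SAP Section 10.0 summarizes every efficacy endpoint by that grouping. None of these says what happens when results disagree.

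**The concern.** Criterion 2.04 is not the complement of 2.03. One negative result is enough for the non-BAM cohort, even when another result from the same person is positive. Only the intermediate-serum item carries a condition that 2.03 is not met; the other four do not.

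All participants receive the same open-label drug without randomization, so cohort membership is the exposure. The primary efficacy objective is the comparison of the two cohorts. If a person who meets a BAM criterion may be counted as a comparator, the contrast can be contaminated, and the reader of the results cannot tell what the groups represent. Descriptive analysis does not remove this, because the group means still depend on who is in each group. Matching is also left to the investigator's discretion, so nothing in the text governs where a dual-eligible participant goes.

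The item that accepts a total of 2337 or below is also in tension with Section 5.4, which warns that "measuring total fecal bile acids alone will miss a subgroup of patients who have features of BAM".

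**Working it through.** N = 24 is 12 + 12 and is stated not to rest on statistical considerations, so there is no sample-size calculation to reproduce. The check is one of logic.

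**Inputs (Protocol Section 6.1).** Let S be serum 7αC4 (ng/mL), T total fecal bile acids (micromoles/48 h) and P primary bile acids (%).

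- 2.03 is met if S ≥ 52.5, or T > 2337, or P ≥ 10, or (P ≥ 4 and T ≥ 1,000).
- 2.04 is met if S ≤ 47.1, or (47.1 < S < 52.5 and no fecal item of 2.03 is met), or T ≤ 2337, or P < 10, or (P < 4 and T < 1,000).

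**Step 1: one result only.** S = 40 meets 2.04 only, S = 50 neither, S = 60 2.03 only. T alone splits cleanly at 2337 and P alone at 10%. There is no overlap.

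**Step 2: full fecal panel, no serum.**

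| | P < 4 | 4 ≤ P < 10 | P ≥ 10 |
|---|---|---|---|
| T < 1,000 | 2.04 only | 2.04 only | both |
| 1,000 ≤ T ≤ 2337 | 2.04 only | both | both |
| T > 2337 | both | both | 2.03 only |

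Six of nine patterns meet 2.03, and five of those six also meet 2.04. Only T > 2337 with P ≥ 10 is BAM and not also non-BAM.

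**Step 3: serum plus fecal results.** S = 40 with T = 3,000 meets both lists, as does S = 60 with T = 1,500. For serum plus a full panel there are 3 × 9 = 27 patterns:

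- S ≤ 47.1: 2.04 is always met, so all six fecal-positive patterns meet both.
- 47.1 < S < 52.5: five meet both, as in Step 2.
- S ≥ 52.5: 2.03 is always met, so every pattern except T > 2337 with P ≥ 10 meets both, which is eight.

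The total is 6 + 5 + 8 = 19 of 27. At the extreme, S = 40, T = 3,000, P = 15 is positive on every fecal item and still qualifies as non-BAM through serum. These are counts of patterns, not of patients.

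**Step 4: illustration from the protocol's own figures.** Section 5.4 reports, for 986 patients with chronic diarrhea, that "26% of patients had elevated total fecal bile acids whereas 46% of patients had fecal primary bile acids" of at least 10%. Assume that elevated means T > 2337, that both percentages come from the same panels, and that the series applies here. Let b be the share positive on both measures (b ≤ 26%) and x ≥ 0 the share positive only on the item combining P ≥ 4 with T ≥ 1,000.

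- Share meeting both lists: (26 − b) + (46 − b) + x = 72 − 2b + x.
- Share fecal-positive: 72 − b + x.
- Minimum, at b = 26 and x = 0: 72 − 52 = 20% of those tested, and 20/46 = 43% of the fecal-positive.
- At b = 20 and x = 0 (b chosen for illustration): 72 − 40 = 32%, and 32/52 = 62%.

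**Step 5: what one participant is worth.** 1/12 = 8.3% of a cohort. If k of the 12 comparators in fact respond as BAM (k is an assumption), the expected contrast is (1 − k/12) of the true one: 0.92, 0.83, 0.75 and 0.67 for k = 1 to 4.

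**Step 6: after the change.** If 2.04 also requires that no available result meets any 2.03 item, the overlap falls from 5 of 9 and 19 of 27 to zero in both.

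**The case against.** The best counter-argument is that a precedence rule already exists. The Section 5.4 sentence pointing to Table 5-2 is worded as a rule for this study and can be read as making any positive result BAM. The serum-only sentence may be a leftover, since the summary of changes says Section 5.4 was updated to cover both tests. A literal reading of Section 6.1 is also impossible elsewhere: its opening line requires every criterion to apply, so sites must already choose a list by its heading. This narrows the defect but does not cure it. The sentence is rationale, the same section contradicts it, and it is not carried into 2.04, Section 7.3 or the SAP.

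Second, few participants may be exposed. Serum is the BAM test named in the screening text, done only where needed, and fecal collection appears as a result already on file from the prior year. The Schedule of Activities is not readable in the copy reviewed. This stands: the number with fecal or discordant results is unknown, and the percentages in Step 4 are illustrations from another population.

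Third, this is a small descriptive pilot, so no error rate or power claim is affected. That is true, but the cohort comparison is still its primary efficacy objective.

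Fourth, removing the overlap does not remove misclassification. A participant with one negative serum result and no fecal test stays non-BAM, although Table 5-2 gives serum 15% sensitivity against fecal weight. That also stands as a limit of the remedy. Table 5-2 also puts the total cutoff at 2,337 or more where 2.03 says above 2337; a rule tied to the 2.03 items is not affected by that difference.

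**Conclusion.** The concern holds. As written, the two lists are not mutually exclusive for anyone with a full fecal panel or with serum and fecal results, and the text allows a participant who meets a BAM criterion into the comparator cohort. This follows from the wording alone and needs no assumption. Participants with a single serum result are not affected.

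The effect on the results cannot be sized. Neither the number of discordant participants nor the direction of any effect on the contrast can be derived from the documents. The 20% and 43% lower bounds rest on the three assumptions in Step 4, and the dilution factors rest on an assumed k. Because the criteria define the trial's only between-group contrast, they need correcting, not merely clarifying.

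**What to change.** - **Protocol Sections 5.4 and 6.1 and the Synopsis:** reconcile them under one stated precedence rule. The rule closest to the Table 5-2 sentence is to add to 2.04 that the participant meets no 2.03 item on any available result in the allowed window. The sponsor should confirm the diagnostic rule.
- **Protocol Section 7.3:** state the same rule for cohort assignment.
- **SAP:** derive cohort from the recorded serum and fecal results by that rule, list participants with discordant results, and repeat the primary descriptive BSFS summary without them.

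The cost is amendment wording, a revised eligibility checklist, one derivation, one listing and one repeated summary. N stays at 24. Non-BAM recruitment might slow, but the documents give no basis for saying by how much. If enrollment is already complete, the SAP steps can still be done.
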